2.4.3. Other Endpoints

Additional endpoints in this study include:

1. Success at 6 months defined as alive on original device or transplanted or explanted for recovery by month 6.
2. Overall Survival on HVAD (Time to Death on original device).

3. Frequency and rates of adverse events per INTERMACS® definition throughout original VAD support.
4. Time on Cardiac Pulmonary Bypass.
5. Perioperative Bleeding and Transfusions (within 48 hours post-op).
6. Length of initial ICU stay.
7. Prevalence and causes of re-hospitalizations (within 6 month period following implantation).
8. Health Status improvement at 6 month, as measured by KCCQ and EuroQol EQ-5D.
9. Functional status improvement, as measured by NYHA and 6-minute walk.
10. Success at 6 months (defined like the primary endpoint) for those screen failures who undergo thoracotomy.

Additional endpoints include observed and change in laboratory, hemodynamics and echocardiogram parameters and neurocognitive testing scores at 6 months. Additional observational endpoints will also be assessed at 6 months. The additional endpoints will be analyzed descriptively, i.e., no inferential analysis will be performed and conclusions will be formulated with caution as these endpoints are not powered.

Time-to-event outcomes will be presented using Kaplan-Meier curves. Quantitative outcomes will be summarized and the corresponding 95% confidence intervals will be derived.

Categorical outcomes will be summarized by presenting frequency and percentage results as well as the corresponding 95% confidence intervals. In particular, adverse events and stroke events summaries will be presented by calculating prevalence (frequency) and event rates (events per patient-year).

Strokes are neurological events specified as an ICVA or an HCVA, as per the current INTERMACS event definition (See Appendix D of the protocol).

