The median time from incision to wire closure of the sternum was 3 hours and 23 minutes and median time on bypass was 70 minutes. Subjects received (median) 1.5 units of packed red blood cells (PRBC). The median parameters for HVAD settings were: 2700 rpm at 3.8 watts, yielding 4.6 L/min of flow. In addition to implant, a number of additional surgical procedures were performed. The most common were patent foramen ovale (PFO)/atrial septal defect (ASD) closures (11/140) and tricuspid valve repair (11/140).

A total of 776 events were reported during the 180 day primary analysis period. Of these 437 (437/776, 56.3%) were INTERMACS defined specific events, and 338/776 (43.6%) events were recorded under the INTERMACS category of “other.” One UADE, chest wall erosion was reported during the 180-day primary endpoint period.

Adverse events defined by INTERMACS criteria during the primary analysis period included the following:

	Date of Event Onset*			
	0-30 Days		31-180 Days	
	Events n	Subjects n (%)	Events n	Subjects n (%)
Bleeding				
Re-operation	23	20 (14.3)	4	4 (2.9)
Transfusion criteria (≥4 within 7 days)	10	10 (7.1)	0	0
Any units after 7 days	31	25 (17.9)	46	20 (14.3)
Infection				
Localized Non-device	20	20 (14.3)	17	17 (12.1)
Driveline Exit Site	5	5 (3.6)	14	11 (7.9)
Sepsis 	3	3 (2.1)	8	7 (5)
Neurological Event				
Ischemic CVA	7	7 (5)	3	3 (2.1)
Hemorrhagic CVA	2	2 (1.4)	2	2 (1.4)
TIA	2	2 (1.4)	5	4 (2.9)
Respiratory Dysfunction				
Dysfunction	26	22 (15.7)	8	5 (3.6)
Arrhythmia				
Ventricular	15	14 (10)	14	11 (7.9)
Supraventricular	25	21 (15)	7	6 (4.3)
Right Heart Failure				
Inotropes	17	17 (12.1)	8	7 (5)
RVAD	3	3 (2.1)	1	1 (0.7)
Device Malfunction				
Pump Failure	3	3 (2.1)	4	4 (2.9)
Non-pump Failure	5	4 (2.9)	14	12 (8.6)
Other				
Arterial Thromboembolism	0	0	2	2 (1.4)
Venous Thromboembolism	4	4 (2.9)	3	3 (2.1)
Renal Dysfunction	8	8 (5.7)	6	5 (3.6)
Psychiatric Episode	5	5 (3.6)	4	4 (2.9)
Myocardial Infarction	0	0	1	1 (0.7)
Hypertension	1	1 (0.7)	0	0
Hepatic Dysfunction	3	3 (2.1)	1	1 (0.7)
Hemolysis event 	1	1 (0.7)	1	1 (0.7)

 A multiple entry (4) of one case was corrected

 Two cases were excluded: 1 case hemolysis < 72 hours post-implant; 1 case hemolysis occurring in the presence of tPA/Integrillin for VAD thrombosis

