## **The FDA Approach**

Most of the medical device guidance documents from the FDA for analyzing events that can happen multiple times specify a specific analytic approach. First, a calculation of the percent of patients who experience at least one event during the first 30 days post implant is presented. Next, a linearized rate is calculated for events that occur after the first 30 days. Summing all of the post 30-day events and dividing by the total patient follow-up intervals after 30 days calculates this. The rate is usually multiplied by 100. The calculation is then the number of events that are estimated to occur in 100 months of follow-up. This is a useful calculation *but* it assumes a constant hazard rate across time. For many events, for example device malfunction, this may be an incorrect assumption.

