2.4.7. Additional Analyses

■ [REDACTED]

[REDACTED]

[REDACTED]

[REDACTED]

[REDACTED]

[REDACTED]

[REDACTED]

[REDACTED]

[REDACTED]

[REDACTED]

[REDACTED]

[REDACTED]

[REDACTED]

[REDACTED]

[REDACTED]

[REDACTED]

[REDACTED]

[REDACTED]

[REDACTED]

[REDACTED]

[REDACTED]

[REDACTED]

[REDACTED]

[REDACTED]

Adverse Events

i) Adverse Events based on INTERMACS definition

The number and percentage of subjects experiencing each specified AE using the INTERMACS definition will be summarized. Any AEs that are not treatment emergent will be listed only.

The incidence of AEs using the INTERMACS definition will be reported in the categories of bleeding (re-hospitalization, re-operation, gastrointestinal (GI)), cardiac arrhythmia (ventricular, supraventricular), device malfunction/failure, hemolysis, hepatic dysfunction, hypertension, infection (localized non-device, sepsis, driveline exit site), myocardial infarction, neurological dysfunction (CT confirmed ischemic cerebral vascular accident (CVA), CT confirmed hemorrhagic CVA , transient ischemic attack (TIA)), pericardial fluid collection, psychiatric

episode, renal dysfunction (acute, chronic), respiratory dysfunction, right heart failure (inotropic therapy, RVAD, inhaled nitric oxide), arterial non-CNS thromboembolism, venous thromboembolism, wound dehiscence, and other event. In addition to the incidence rate, the number of events and the event rate per patient year will be reported for each INTERMACS-defined adverse event. For the incidence rate, a subject will only be counted once per each INTERMACS-defined category and counted once per each INTERMACS-defined sub-category.

No statistical inference will be performed on adverse events.

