2.5. Long-Term Follow-up Analyses

Adverse events through data cut will be included in the initial study results report. No other long term analysis will be included at that time. All data will be included in the final report.

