1. Calculate the patient-years contributed by each subject. The time in the study starts at enrollment. The end date would be the last follow-up date (end of study), unless the subject has an explant (when the pump is removed, turned off, or exchanged), dies, or is lost to follow-up prior to the end of study. The patient years are calculated as (date of explant or death or last follow-up or end of study – date of enrollment + 1)/365.24. When the number of days is negative, the value will be missing for the patient-years.
2. Sum the patient-years across all subjects in the study. This is the denominator.
3. Sum the total number of events for a particular adverse event (prior to exchange). If a subject has patient-years that is missing, the AEs will not be counted for these subjects (e.g., subjects who have ongoing AEs that are entered into the database, an exchange after the AE but prior to enrollment).
4. The adverse event rate per patient-year = (Sum of the total number of events for the particular adverse event (prior to exchange))/(Sum of the patient-years across all subjects in the study).

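### Adverse event rates pool all time on the original device, so rates of surgery-related events fall as follow-up lengthens and late-rising events are masked

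*SAP*

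**What the plan says.** SAP 2.4.3, item 3, sets a single window for adverse events: "Frequency and rates of adverse events per INTERMACS® definition throughout original VAD support". SAP 3.2, in the adverse event rate calculation, sums all events before exchange and divides by one exposure total: "Sum the patient-years across all subjects in the study. This is the denominator". Exposure is counted from enrollment rather than implant: "The time in the study starts at enrollment". SAP 2.5 leaves the length of follow-up open in the first report: "Adverse events through data cut will be included in the initial study results report".

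SAP 2.4.7 adds summaries that are not rates: "The number and percentage of subjects experiencing each specified AE using the INTERMACS definition will be summarized". It also gives event counts by category and states that there will be no inference on adverse events. SAP 2.4.3, item 5, has a separate bleeding and transfusion endpoint limited to the first 48 hours.

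No readable passage splits adverse events by time since implant. A block of SAP 2.4.7 before the adverse event text is redacted, as are the protocol's additional endpoints, so a split there cannot be excluded.

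The maximum follow-up also differs: 2.5 years after implant in Protocol 7.2, 5 years in SAP 1.2.

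**The concern.** The study evaluates an implant technique, and Protocol 12.1 expects it to reduce bleeding, infection and right heart failure. Bleeding and right heart failure are concentrated soon after surgery in the sponsor's earlier studies. When an event is front-loaded, each extra month on the device adds exposure with few events, so events per patient-year fall although nothing about the operation has changed. The figure then depends on the data-cut date and on how quickly subjects are transplanted. For an event that becomes more frequent with time on the device, pooling does the opposite: quiet early exposure masks the late rate.

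Comparison is affected too. Protocol 4.2.3 introduces its main US sternotomy table with "Adverse events defined by INTERMACS criteria during the primary analysis period included the following" and splits it into days 0-30 and 31-180. A rate pooled over all support cannot be placed directly beside it. The registry protocol in Appendix A describes a summary for recurring events that keeps the early period apart: "First, a calculation of the percent of patients who experience at least one event during the first 30 days post implant is presented". A linearized rate is used there only after day 30.

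**Working it through.** 1. International study (Protocol 4.2.1). Exposure is 22.3, 13.8 and 11.7 patient-years for 0-180, 180-365 and >365 days, in total 47.8. Rate = events / patient-years. The last two columns pool cumulatively, as SAP 3.2 does.

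| Event | 0-180 d | 180-365 d | >365 d | Pooled to 365 d | Pooled, all |
|---|---|---|---|---|---|
| Bleeding | 14/22.3 = 0.63 | 3/13.8 = 0.22 | 1/11.7 = 0.09 | 17/36.1 = 0.47 | 18/47.8 = 0.38 |
| Pump replacement | 6/22.3 = 0.27 | 0 | 1/11.7 = 0.09 | 6/36.1 = 0.17 | 7/47.8 = 0.15 |
| Infection | 9/22.3 = 0.40 | 7/13.8 = 0.51 | 4/11.7 = 0.34 | 16/36.1 = 0.44 | 20/47.8 = 0.42 |
| Hemorrhagic stroke | 0 | 1/13.8 = 0.07 | 3/11.7 = 0.26 | 1/36.1 = 0.03 | 4/47.8 = 0.08 |

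The printed period rates reproduce, apart from rounding (1/11.7 = 0.085 is printed as 0.08). Pooled bleeding falls by (0.63 - 0.38)/0.63 = 40% in the same cohort of 50. Infection hardly moves. Hemorrhagic stroke runs at 0.26 after one year but shows as 0.08 when pooled.

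2. ADVANCE counts (Protocol 4.2.3, 140 implants), days 0-30 then 31-180: re-operation for bleeding 23 and 4; right heart failure on inotropes 17 and 8; respiratory dysfunction 26 and 8. The early window is 30 days and the late one 150. Exposure by period is not printed, so it must be assumed. Early exposure is at most 140 × 30 days = 11.5 patient-years. Late exposure is between 88 × 150 days = 36.1 (only those on the original device at day 180) and 140 × 150 days = 57.5.

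- Re-operation for bleeding: 23/11.5 = 2.00 early; 4/57.5 to 4/36.1 = 0.07 to 0.11 late.
- Right heart failure on inotropes: 17/11.5 = 1.48 early; 8/57.5 to 8/36.1 = 0.14 to 0.22 late.
- Respiratory dysfunction: 26/11.5 = 2.26 early; 0.14 to 0.22 late.

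3. Projection of the pooled re-operation rate, under two sets of assumptions. Both carry the day 31-180 rate forward unchanged.

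- Exponential loss from the original device to 88/140 at 180 days (0.493 years): λ = -ln(88/140)/0.493 = 0.942 per year. Exposure per subject, (1 - exp(-λt))/λ, is 0.079 years at 30 days, 0.394 at 180 days and 0.961 at 2.5 years. Late rate: 4/(140 × 0.315) = 0.091. Pooled at 180 days: 27/(140 × 0.394) = 0.49. Pooled at 2.5 years: [27 + 0.091 × 140 × (0.961 - 0.394)]/(140 × 0.961) = 34.2/134.5 = 0.25.
- A subject who stays on the device to time T: [23/140 + late rate × (T - 0.082)]/T, with late rate 0.070 to 0.111. At T = 0.493: 0.39 to 0.43. At T = 2.5: 0.13 to 0.17.

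**The case against.** Several counter-arguments stand.

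- A reader might infer that the rate is invalid unless the hazard is constant. It is not: events over person-time is a proper descriptive average under any hazard. Constancy matters only when the figure is read as a steady risk or compared across different follow-up lengths. The caution on constant hazard in Appendix A concerns the rate after day 30, which the same text calls useful, and it describes one registry method among several.
- A reader might infer that longer follow-up makes the technique look safer throughout. The international data do not support this: infection is flat and hemorrhagic stroke rises.
- A reader might infer that no sternotomy comparison is possible. Protocol 4.2.2 reports ReVOLVE as one pooled rate per event over 252.6 patient-years (bleeding 0.40, right heart failure 0.10), with thoracotomy patients left out. The SAP rate can be set beside that table, with the proviso that mean support there was 363 days.
- A reader might infer that safety cannot be assessed at all. Percent of subjects and event counts do not fall with follow-up. Bleeding within 48 hours, initial ICU stay, 6-month re-hospitalizations and the 6-month primary endpoint all have fixed windows, and SAP 2.5.1 plans descriptive summaries at 12, 18 and 24 months.

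What these do not answer: percent of subjects and event counts have no readable time split and grow with follow-up, and the 48-hour endpoint covers one event type and not days 3-30. Nothing readable isolates days 0-30 for all event types. Event dates are collected, so a split could be tabulated later. That makes it cheap, but does not make it pre-specified.

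**Conclusion.** The point holds for the readable text and for surgery-related events. Pooled bleeding falls from 0.63 to 0.38 per patient-year on the protocol's own data, with no modelling. For re-operation bleeding the modelled fall is from about 0.4-0.5 at 180 days to about 0.13-0.25 at 2.5 years. That range rests on assumed exposure and on extending a late rate based on four events, so the direction is firmer than the size. Infection is roughly unaffected, and late-rising events such as hemorrhagic stroke (0, 0.07, 0.26) are masked rather than diluted.

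Because adverse events are not tested, the effect is on how the safety display is read and not on any formal conclusion. Two limits remain: the redacted part of SAP 2.4.7 may contain a split, and the time base of the pooled rate is unsettled while the two maximum follow-up statements disagree.

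**What to change.** In SAP 2.4.7 and in the rate calculation of SAP 3.2, add reporting by period on the original device, timed from implant:

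- Days 0-30 and 31-180: number and percent of subjects with each INTERMACS event, and event counts, in the layout of the ADVANCE table.
- Days 31-180 and after day 180: events per patient-year, with only that period's exposure in the denominator.
- Keep the pooled rate alongside, with total exposure stated, for use beside ReVOLVE.

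Reconcile the 2.5-year limit in Protocol 7.2 with the 5-year limit in SAP 1.2. If redacted text already specifies a period split, align the single denominator in SAP 3.2 with it.

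The cost is SAP wording and extra table columns; no new data are needed. The early figures will look less favourable than the pooled rate.

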### Competing Outcomes

Depictions of a single time-related event do not take into account other events. For example, a depiction of death would assume that transplantation does not exist. Patients are censored at time of transplant. If informative censoring does not exist (i.e., if patients are not transplanted due to impending death but instead selected at random for transplant), then the depiction can be thought of as the natural history of mortality after device implant. In reality, this rarely occurs, since patients are usually selected at a given time because of medical necessity. This informative censoring complicates the interpretation of this single event depiction.

Alternatively, one may wish to estimate the simultaneous time-related probability of mutually exclusive events. Competing outcomes estimation allows the time-related probability of actually experiencing each of these events. At any point in time, a patient has either experienced one of the three events or he/she is alive and waiting for one of the events to occur. A probability can be assigned to each of these four possible states and the sum of the four probabilities will be equal to one at each point in time. The non-parametric estimation of these probabilities is an adaptation of the Kaplan-Meier method. In the standard use of the Kaplan-Meier methods, event probabilities are accumulated across time. In competing outcomes analysis, the combined event is

analyzed and then probabilities are accumulated separately according to which event occurred.

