3.2. Definition of Calculated Variables

1. Basic Variable Definitions

- Age will be calculated as the informed consent date minus the date of birth divided by 365.24 [Age=(ICF Date-DOB)/365.24]. Age will be rounded down to the nearest whole number
- Body mass index (BMI; kg/m²) is calculated as: weight (kg) / [height (m)]², rounded to one decimal place.
- Body surface area (BSA; m²) is calculated as:
$$BSA = (W * H / 3600)^{0.5}$$
where W = weight in kg and H = height in cm
- Weight will be displayed in kilograms (kg), height will be displayed in centimeters (cm), and temperature will be displayed in Celsius (C).
- Weights, heights, or temperatures recorded in alternate units will be converted to the units being displayed using standard conversion formulas.
- Length of Operative Time (Hours) = Time end of surgery for implantation – Time start of surgery for implantation
- Length of Initial Hospital Stay (Days) = Date of discharge following device implantation – date of hospitalization prior to device implantation + 1
- For days on or after the device is implanted:
Relative Study Day (Rel Day) = Date of Assessment – date of induction of anesthesia to implant of the study device + 1.
For days before the device is implanted:
Relative Study Day (Rel Day) = Date of Assessment – date of induction of anesthesia to implant of the study device.
- Days survived = Date of death/date of event for censoring – date of induction of anesthesia to implant of the study device + 1

- Days of hospitalization = Date of hospital discharge – Date of admission + 1
- Cumulative days of hospitalization after initial hospitalization is the sum of length of hospital stays after initial hospitalization.
- Days to first explant = Date of explant – date of induction of anesthesia to implant the initial study device + 1
- Days to first exchange = Date of exchange – date of induction of anesthesia to implant the initial study device + 1
- Days to transplant = Date of transplant – date of induction of anesthesia to implant the initial study device + 1
- Change from baseline (CFB) = Visit value – Screening/Pre-Implant value

2. Calculation of adverse event rate per patient-year

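### Time to death on the original device is planned as a Kaplan-Meier curve with no named censoring events and no cumulative incidence; its complement would exceed the proportion who actually die on the device

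*SAP*

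**What the plan says.** SAP 2.4.3 lists ten additional endpoints. The second is "Overall Survival on HVAD (Time to Death on original device". For all of them the display rule is "Time-to-event outcomes will be presented using Kaplan-Meier curves", and the section limits their role: "no inferential analysis will be performed and conclusions will be formulated with caution as these endpoints are not powered".

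The only visible trace of a censoring rule is the days-survived formula in SAP 3.2, which starts from "Date of death/date of event for censoring" and names no events. Other sections show what happens in practice:

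- Participation ends at induction of anesthesia for transplant (Protocol 7.2, SAP 1.2).
- INTERMACS stops following a patient once transplanted (Appendix A, A.1.1).
- Subjects explanted for recovery before month 6 leave at their next scheduled visit (Protocol 7.2).
- Subjects with an exchange stay in follow-up, but they are no longer on the original device. SAP 3.2 stops adverse-event patient-years when the pump is removed, turned off or exchanged.

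Appendix A, A.5.5, discusses a curve for death alone. It says "Patients are censored at time of transplant" and explains that this is harmless only if selection for transplant is random. It continues: "In reality, this rarely occurs, since patients are usually selected at a given time because of medical necessity", and concludes: "This informative censoring complicates the interpretation of this single event depiction". It then offers an alternative: "Competing outcomes estimation allows the time-related probability of actually experiencing each of these events". Section A.5.6 plans that joint display of death, transplant and explant for the registry's own analyses. SAP 2.5.1 plans summaries at 12, 18 and 24 months.

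**The concern.** These are bridge-to-transplant patients, so leaving the device alive by transplant is the expected course. In both prior cohorts used below, transplants outnumber deaths on the device. With that many competing exits, a Kaplan-Meier curve for death that censors them estimates mortality in a setting where nobody leaves by another route. It does not estimate the share of patients who die on the device, although a clinician will probably read it that way, and the difference grows with follow-up.

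A second problem is that the rule is not written down. Two analysts could treat explant and exchange differently and obtain different curves, and the text does not settle which is intended.

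What is at stake is the meaning of one descriptive result, mainly at the 12 to 24 month reports. No hypothesis test depends on it.

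**Working it through.** The SAP gives no figure for this endpoint, so there is none to reproduce. The sample size of 145 belongs to the primary binomial test and does not depend on this point. It checks out: requiring at least 121 successes of 145 gives one-sided alpha 0.0494 and power 84.3% at 86% success.

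**1. Direction.** Let h(u) be the hazard of death on the device, K(u) the Kaplan-Meier survival with other exits censored, and A(u) the probability of still being alive on the original device. Then

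- 1 − KM = ∫ K(u) h(u) du
- cumulative incidence = ∫ A(u) h(u) du

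Because K(u) ≥ A(u), 1 − KM is never below the cumulative incidence. They are equal only if no competing exit precedes a death.

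**2. Earlier US trial at 180 days (Protocol 4.2.3, n = 140).**

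- Deaths on the original device: 6
- Exchanges: 5 alive + 2 dead = 7
- Transplanted or explanted: 127 successes − 88 on the original device = 39
- Remaining: 88; check 6 + 7 + 39 + 88 = 140

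Cumulative incidence = 6/140 = 4.3%.

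With constant cause-specific hazards over the window, H = −ln(88/140) = 0.4643. Deaths are 6 of 52 exits, so 1 − KM = 1 − exp(−0.4643 × 6/52) = 5.2%. The gap is 0.9 points. Bounds that do not assume constant hazards are 6/140 = 4.3% (all deaths before any other exit) and 6/94 = 6.4% (all deaths after the other 46 exits).

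**3. The same hazards carried to 24 months (assumption).** With u = 730.5/180 = 4.058:

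- 1 − KM = 1 − exp(−0.4643 × 6/52 × 4.058) = 19.5%
- cumulative incidence = (6/52) × [1 − exp(−0.4643 × 4.058)] = 9.8%

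The gap is about 10 points. Counting 6 months as exactly 180 days gives 19.3% against 9.7%.

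**4. ReVOLVE registry (Protocol 4.2.2).** Reported actuarial success is 87%, 85% and 79% at 6, 12 and 24 months, so failure rises by 13, 2 and 6 points over the three intervals. Transplants and recoveries are 56 + 3 = 59 over 252.6 patient-years, a rate c = 0.2336 per year.

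Assume that the curve is Kaplan-Meier with those exits censored, that c is constant, and that failures are spread evenly within each interval. Each increment is then weighted by the average chance of not yet having left, (e^(−ca) − e^(−cb)) / [c(b − a)], for an interval from a to b years:

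| Interval (months) | Failure (points) | Weight | Contribution (points) |
|---|---|---|---|
| 0–6 | 13 | 0.944 | 12.3 |
| 6–12 | 2 | 0.840 | 1.7 |
| 12–24 | 6 | 0.706 | 4.2 |
| Total | 21 | | 18.2 |

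This gives 13% against 12.3% at 6 months and 21% against 18% at 24 months. The gap is smaller than in step 3 because the reported risk falls mostly in the first 6 months, before many transplants occur.

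**The case against.** The strongest reply is that little depends on this. It is one of ten additional endpoints, none is tested, and the SAP promises caution. Kaplan-Meier matches most of the survival benchmarks that the protocol cites. In the US trial the reported Kaplan-Meier survival at 180 days, on a definition that counts transplant as survival, was 93.9%. That is 6.1% failure against 8/140 = 5.7% deaths, a gap of 0.4 points. The SAP also plans crude 6-month success proportions, a later analogue of the primary endpoint, and a disposition summary with reasons for discontinuation.

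Most of this stands. It limits the point to a refinement of a descriptive display. It does not remove it: success composites do not isolate death on the original device, and a disposition table does not give its probability by time.

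Several stronger readings are tempting, and the documents do not support them:

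- **That the SAP specifies censoring at transplant and exchange.** It names no events. The rule is inferred from where follow-up ends and from the restriction to the original device.
- **That Appendix A says Kaplan-Meier overstates death.** It gives no direction and does not mention exchange. The excess over the crude proportion comes from step 1. Informative censoring is a separate matter: if sicker patients are transplanted first, Kaplan-Meier could understate the risk in a world without transplant.
- **That Kaplan-Meier is certainly the only display.** SAP 2.4.7 and the protocol's list of additional endpoints are largely redacted.
- **That ReVOLVE implies a much larger gap.** A constant hazard of 43/252.6 = 0.170 per year predicts 8.2% failure at 6 months and 28.9% at 24. The registry reports 13% and 21%, so that model does not fit its own source.

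**Conclusion.** The point holds as a gap in specification and presentation. In the visible SAP, time to death on the original device has a Kaplan-Meier display, no named censoring events and no competing-outcomes estimate. If transplant, explant and exchange are censored, as the follow-up rules and the endpoint's wording imply, 1 minus Kaplan-Meier would exceed the proportion who die on the device.

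The excess is about 1 point at 6 months, which matters little. At 24 months a fair range is about 3 to 10 points. The lower figure reads ReVOLVE's success curve as Kaplan-Meier with transplants censored, which the protocol does not state, and holds its exit rate constant. The upper figure extrapolates 6 deaths in 180 days at constant hazards and is best taken as an upper illustration, given how early the risk fell in ReVOLVE.

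The primary conclusion is untouched. Nothing in the documents makes this survival curve a headline result.

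**What to change.** In SAP 2.4.3:

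- Name transplant, explant for recovery and exchange as competing events for death on the original device.
- Add cumulative incidence estimates for death on the original device, transplant, explant for recovery and exchange beside the Kaplan-Meier curve, read at 6, 12, 18 and 24 months.
- Report the proportion dying on the device from the cumulative incidence estimate. Keep Kaplan-Meier, with its censoring events stated, for comparison with earlier reports.

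The data are already planned: Protocol 9.2.5 records outcome type and transplant date, and SAP 3.2 derives days to explant, exchange and transplant. The cost is a sentence or two, one extra figure and slightly more analysis work. Sample size, alpha and the primary analysis do not change.
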